5.6.1. Permitted Concomitant Therapies

Permitted concomitant medications include lid hygiene, warm compresses and artificial tears or any medication not mentioned in the exclusion criteria provided the subject has been on a stable dose for at least 4 weeks prior to the Screening Visit. Patients should be instructed not to use ophthalmic preparations 2 hours prior to each study visit.

5.6.2. Prohibited Concomitant Therapies

The following treatments will not be permitted during the study (from the Baseline Visit through Visit 7):

- Administration of live or live-attenuated vaccines.
- Use of eyelash growth medications.
- Topical, inhaled, intra-articular, or intra-ocular corticosteroids.
- Any systemic corticosteroids, immunosuppressants, immunomodulators, or biologic agents for a concomitant condition (eg, rheumatoid arthritis being treated with a TNF- α drug).
- Any investigational drug, device, or procedure administered as part of a research study.

If any prohibited medication is taken during the study, all pertinent information will be recorded in source documents and the electronic case report form (eCRF). The designated study medical monitor (MM) must be informed immediately and will determine whether to continue the subject in the study in collaboration with the sponsor.

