3. STUDY DESIGN

3.1. Overall Design

This is a multicenter, multiple dose, open-label study to examine the efficacy of Acthar in adult subjects 18 years of age or older with a diagnosis of keratitis sicca. Up to 36 subjects with severe or recalcitrant keratitis who did not respond or tolerate treatment with topical cyclosporine or any immunosuppressant to treat keratitis will be enrolled. Subjects who meet entry criteria will be treated with Acthar 1 mL (80 units [U]) subcutaneously (SC) 2x (twice) per week for 12 weeks, followed by a 4 week taper period of 40 U 2x/week for 2 weeks then 40 U 1x/week for 2 more weeks. Subjects will be reassessed at an in-clinic safety visit, 4 weeks after the last treatment dose for AE assessments, and concomitant medication use. Endpoints will be measured at Baseline and all other visits.

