4.2. Exclusion Criteria

A subject is ineligible for study participation if the subject meets any of the following criteria at the Screening or Baseline Visit:

1. Subject is from a vulnerable population, as defined by the US CFR Title 45, Part 46, Section 46.111(b) and other local and national regulations, including but not limited to, employees (temporary, part-time, full time, etc.) or a family member of the research staff conducting the study, or of the sponsor, or of the clinical research organization, or of the IRB/IEC;
2. Have any ocular condition that, in the opinion of the investigator, could affect study parameters including, but not limited to, glaucoma, diabetic retinopathy, blepharitis, meibomian gland disease, lid margin inflammation, ocular allergies, follicular conjunctivitis, iritis, uveitis, neuropathic pain and/or active ocular inflammation not related to keratitis;
3. Have a history of laser-assisted in situ keratomileusis (LASIK) or similar type of corneal refractive surgery within 12 months prior to the Baseline visit, and/or any other ocular surgical procedure (eg, cataract surgery, eyelid surgery) within 12 months prior to the Baseline Visit; or any scheduled ocular surgical procedure during the study phase;
4. Have active or any history of ocular herpes; and other ocular infection within 30 days prior to the Baseline visit;
5. Have current punctal plugs (within 30 days prior to Screening visit), punctal occlusion, or history of nasolacrimal duct obstruction;
6. Be unwilling to avoid wearing contact lenses for 7 days prior to the Screening visit and for the duration of the study phase;
7. Have best corrected visual acuity < 0.7 Logarithm of the Minimum Angle of Resolution (logMAR) in each eye at the Screening and Baseline Visits;
8. Use prohibited prescription or over-the-counter (OTC) medications or devices and be unable to discontinue their use for the required period before entry into the study as follows:

- a. Ophthalmic cyclosporine (Restasis®) or ophthalmic lymphocyte function-associated antigen-1 (LFA-1) antagonist (Xiidra®): 12 weeks prior to the Screening visit;
- b. Corticosteroids (topical and systemic), ocular autologous serum, antibiotics (topical and systemic), mast cell stabilizers (topical and systemic), vasoconstrictors (topical and systemic): 30 days prior to the Screening visit;

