19. Subject is under treatment with any corticosteroids, immunosuppressants, immunomodulators, or biologic agents for a concomitant condition (eg, rheumatoid arthritis under treatment with a tumor necrosis factor- alpha [TNF- α] drug). Subjects are specifically excluded for any of the following;
 - a. Subject has received intraocular or periocular corticosteroids within 30 days prior to Baseline Visit;
 - b. Subject has received Ozurdex® (dexamethasone implant) within 6 months prior to the Baseline Visit;
 - c. Subject has received intravitreal anti-VEGF therapy within 45 days of the Baseline Visit with Lucentis® (ranibizumab) or Avastin® (bevacizumab) or has received anti-VEGF Trap (aflibercept) within 60 days of the Baseline Visit;
 - d. All others, subject has received treatment within 30 days prior to baseline;
20. Subject has any known contraindication(s) to [Acthar® Gel Package Insert, 2019](#) including, but not limited to:
 - a. Any known history of scleroderma, osteoporosis, or ocular herpes simplex. For the purposes of this study, osteoporosis is defined as evidence of current vertebral or long bone fracture, or lumbar T-score > 2.0 standard deviations (SD) below the mean of the reference population;
 - b. Any primary adrenocortical insufficiency, or adrenal cortical hyperfunction,
 - c. Any current congestive heart failure (defined as New York Heart Association Functional Class III to IV),
 - d. Peptic ulcer (within 24 weeks prior to the Screening Visit);
 - e. Recent major surgery (within 24 weeks prior to the Screening Visit);
21. Subject has a clinically significant infection requiring administration of intravenous antibiotics or hospitalization in the 4 weeks prior to the Screening Visit or between the Screening Visit and the first dose of study drug;
22. Subject has known immune-compromised status (not related to disease/condition under study), including but not limited to, individuals who have undergone organ transplantation or who are known to be positive for the human immunodeficiency virus;
23. Subject has any solid tumor malignancy currently diagnosed or undergoing therapy, or has received therapy for any solid tumor malignancy in the 5 years prior to the Screening Visit; with the exception of treated and cured basal cell carcinoma, treated and cured squamous cell carcinoma of the skin, and treated and cured carcinoma in situ of the cervix;

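### The bar on systemic immunosuppressive drugs is tied to a concomitant condition, so a start for the keratitis itself is off the prohibited list, and no responder rule covers it

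*Combined protocol and SAP*

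**What the plan says.** Section 5.6.2 lists treatments not allowed from Baseline through Visit 7. One line bars "Topical, inhaled, intra-articular, or intra-ocular corticosteroids" with no limit by indication. The next bars "Any systemic corticosteroids, immunosuppressants, immunomodulators, or biologic agents for a concomitant condition", with rheumatoid arthritis treated with a TNF drug as its example. If a prohibited drug is taken, the use is recorded, the medical monitor is told at once, and continuation is decided with the sponsor.

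The stem of Exclusion 19 has the same limit: "Subject is under treatment with any corticosteroids, immunosuppressants, immunomodulators, or biologic agents for a concomitant condition". Its sub-items name particular ocular treatments, and 19d adds all others received within 30 days before Baseline.

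Exclusion 8b names "Corticosteroids (topical and systemic), ocular autologous serum, antibiotics (topical and systemic") and further classes, for 30 days before Screening and whatever the indication. Exclusion 8 is framed as a washout: it applies to subjects who use the listed products and would "be unable to discontinue their use for the required period before entry into the study".

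Section 5.6.1 permits some supportive measures and "any medication not mentioned in the exclusion criteria provided the subject has been on a stable dose for at least 4 weeks" before Screening.

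Section 3.1 describes the population as subjects "who did not respond or tolerate treatment with topical cyclosporine or any immunosuppressant to treat keratitis will be enrolled".

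On analysis, section 2.3 makes the IDEEL responder proportion the primary outcome. Section 8.2 puts in the mITT set every dosed subject with any postbaseline efficacy data, and removes major deviations, which it does not define, from the Per-Protocol set. Section 8.3.1 runs all efficacy analyses on mITT. None of these mentions added therapy. Section 8.3 leaves further detail to a separate SAP.

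**The concern.** The two neighbouring lines of section 5.6.2 are built differently. Local and inhaled corticosteroids are barred outright; the systemic classes are barred by indication. A reader applying the list literally will take the limit to mean something: a biologic for rheumatoid arthritis is caught, while the same biologic or an oral corticosteroid begun because the keratitis is worsening is not. That is the one indication under which the added drug acts directly on the efficacy outcome.

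Two things follow. First, the medical-monitor step in section 5.6.2 is triggered only by a prohibited drug, so it is not clearly triggered here. Second, there is no control arm in which the same added therapy would show up, so benefit from the added drug cannot be separated from benefit from Acthar. An analysis rule written only around prohibited medication would also miss these subjects.

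**Working it through.** The plan has no calculated figure to reproduce here: section 8.1 sets the sample size empirically and gives no response rate, alpha or power. The check is a reading of the rules against one case, followed by simple arithmetic.

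**Case: a systemic agent of a listed class is started after Baseline for the keratitis.**

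- Section 5.6.2, systemic line: not caught, because the indication is the study disease.
- Section 5.6.2, local and inhaled corticosteroid line: not caught, because the route is systemic.
- Exclusion 19: an entry criterion, so it does not govern on-study starts; its stem has the same limit by indication.
- Exclusion 8b: covers systemic corticosteroids for any indication, but only as a washout before Screening. Exclusion 8 does not name systemic non-steroid immunosuppressants as a class.
- Section 5.6.1: not affirmatively permitted, because a new drug cannot have been stable for 4 weeks before Screening. But the section says what permitted medications include, and does not say that everything else is prohibited.

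The drug is thus on neither list. For a systemic immunosuppressant already taken stably for keratitis, section 5.6.1 turns on whether the drug is mentioned in the exclusion criteria, which leads back to Exclusion 19 and its limit.

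**What the analysis text then does.** The subject was dosed and has postbaseline data, so is in mITT (section 8.2). The responder outcome (section 2.3) and the efficacy analysis (section 8.3.1) contain nothing that sets aside values after added therapy. By default the observed IDEEL score is used.

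**Size.** Inputs: 30 analysable subjects and 36 as the upper limit on enrolment (sections 8.1 and 3.4). If k subjects become responders only because of the added drug, the proportion rises by k/n.

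- n = 30: 1/30 = 3.3 points per subject.
- n = 36: 1/36 = 2.8 points per subject.

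For illustration only, assume 12 of 30 would respond without added therapy. Exact 95% limits are the 0.025 quantile of Beta(x, n − x + 1) and the 0.975 quantile of Beta(x + 1, n − x).

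| Extra responders k (assumed) | x/30 | Proportion | Exact 95% CI |
|---|---|---|---|
| 0 | 12/30 | 40.0% | 22.7 to 59.4 |
| 1 | 13/30 | 43.3% | 25.5 to 62.6 |
| 3 | 15/30 | 50.0% | 31.3 to 68.7 |
| 5 | 17/30 | 56.7% | 37.4 to 74.5 |

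Both the 12 and the values of k are assumptions. The shift of k/30 does not depend on the starting count.

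**The case against.** The case against a strong reading is good, and several inferences a reader might draw do not hold.

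- *That the protocol allows these drugs for keratitis.* It does not say so. Under section 5.6.1 a newly started drug fails the stability condition whatever its indication. The status is unclear, not released.
- *That the entry criteria contradict each other.* Exclusions 8b and 19 must both be satisfied, so they overlap and the stricter applies. Item 19d can be read as reaching every listed class, since 19a to 19c state no indication. The weakness lies mainly in the on-study list.
- *That such a subject has no deviation and stays in the Per-Protocol set.* Section 8.2 does not define a major deviation, so this cannot be read from the text either way.
- *That the plan counts the improvement as an Acthar response.* No sentence says so; it follows from silence, and the separate SAP could set a rule.
- *That the responder rate is inflated by 3 to 17 points.* That range (1/30 to 5/30) needs an assumed 1 to 5 affected subjects, every one of whom would otherwise have been a non-responder. The documents support neither part. Section 3.1 speaks of past treatment failure or intolerance, and nothing says how often systemic therapy would be added.

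It is also fair that the missing analysis rule is wider than this wording: it applies equally to drugs that section 5.6.2 does prohibit.

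What remains is that the list is unclear for the indication that matters most to efficacy, and that the text supplied has no rule for the result. Deferral to the SAP answers this only in part: section 8.3 requires it to be final before database lock, and in an open-label study responses may be known by then.

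**Conclusion.** The concern holds in a limited form. It rests on the wording of sections 5.6.1 and 5.6.2 and Exclusions 8b and 19, and on the absence of an added-therapy rule in sections 2.3, 8.2 and 8.3.1. The possible bias is towards a higher responder proportion: 3.3 points at n = 30, or 2.8 at n = 36, for each subject who responds only because of the added drug. The total cannot be estimated, because the number of such subjects is unknown and may be zero. The point merits correction because the outcome is a single-arm proportion in a small sample and the remedy needs no new data.

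**What to change.** 1. Reconcile sections 5.6.1 and 5.6.2 with Exclusions 8b and 19, so that the text states whether the bar on systemic corticosteroids, immunosuppressants, immunomodulators and biologics depends on indication. Which way to settle it is the sponsor's clinical choice.
2. Independently of that choice, state in section 8.3.1 that, once any of these drugs is started or increased after Baseline, later IDEEL assessments count as non-response in the primary mITT responder analysis. Add a sensitivity analysis that uses the observed values regardless. The primary rule is one choice among several, made because a single-arm study cannot apportion the benefit; the sensitivity analysis shows how much depends on it. Framing the rule by drug class, not by prohibited status, also covers the drugs already barred.
3. State in section 8.2 that such use is a major deviation for the Per-Protocol set where the reconciled text prohibits it. Use that the text permits should not be called a deviation.

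The cost is protocol wording and one analysis rule with its sensitivity analysis. Section 5.6 already collects dates, dose, route and indication. The downside is a slightly lower responder rate, since a subject who would have responded to Acthar alone but received such a drug is counted as a non-responder.

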6.2. Subject Discontinuation/Withdrawal from the Study

Subjects may withdraw from the study at any time at their own request, or may be withdrawn at any time at the discretion of the investigator for safety, behavioral, compliance, or administrative reasons.

If the subject withdraws consent for disclosure of future information, the sponsor may retain and continue to use any data collected before such withdrawal of consent. If a subject withdraws from the study, the subject may request destruction of any samples taken and not tested and the investigator must document this in the site study records.

The reason for study discontinuation/withdrawal will be recorded. A subject may be discontinued from the study for the following medical or administrative reasons:

Withdrawal by Subject

Subjects will be free to discontinue from the study at any time.

Adverse Event

If a dosed subject suffers an adverse event (AE) that, in the judgment of the investigator, sponsor, or MM; presents an unacceptable consequence or risk to the subject, the subject will be discontinued from study drug.

Death

In the event that a subject dies during the study, death will be the reason for discontinuation.

Lost to Follow-up

Every effort should be used to maintain contact with subjects during their participation in the study. A subject may be considered lost to follow-up if there is no response to at least 3 attempts to reach the subject by phone and no response to a certified letter (or equivalent) sent to the last known address of the subject, if possible. Efforts to contact the subject should be noted in the source documentation.

Met Withdrawal Criteria

Discontinuation for safety and/or tolerability issues is outlined in Section [6.1](#).

Other

If the above reasons are not applicable, please use the “Other” option in the eCRF and provide the appropriate reason for subject withdrawal.

7. STUDY ASSESSMENTS AND PROCEDURES

7.1. Efficacy Assessments

Efficacy assessments will be evaluated at times specified in the Schedule of Study Events ([Table 1](#)). Below is a general instruction for the administration of these assessments. Specific instructions and equipment specifications (where appropriate) will be provided in a separate document.

7.1.1. Ophthalmic Examination

An ophthalmic examination will be completed at specified times during the study and will include the following:

- Best corrected visual acuity (BCVA) measured using the using the Early Treatment Diabetic Retinopathy Study (ETDRS) chart ([Hilton, 2009](#)).
- Intra-ocular pressure (IOP) will be measured using Goldmann Applanation Tonometry ([Ramakrishnan, 2009](#)).
- Complete Slit lamp examination (including evaluation of the cornea and lens and grading of superficial puncta).
- Undilated funduscopic evaluation.

7.1.2. Patient-reported Outcomes (PROs)

The following 4 questionnaires were used to assess quality of life (QOL) measures ([Sheppard, 2014](#)):

Impact of Dry Eye on Everyday Life (IDEEL) Questionnaire: The IDEEL comprises 57 questions and 3 modules: the impact on daily life module (activity/work limitations and emotional impact), the treatment satisfaction module, and the symptom bother module. Each module is scored from 0 to 100; higher scores on the impact on daily life and treatment satisfaction modules indicate a better quality of life (QOL) and higher treatment satisfaction. In contrast, higher scores on the symptom bother module indicate more bothersome dry eye symptoms. A 12-point difference in symptom bother module scores indicates a clinically important change in bothersome dry eye symptoms ([Grubbs, 2014](#)).

Ocular Discomfort Score (ODS): The ODS is a scale in which subjects are asked to subjectively rate 5 areas of ocular discomfort: ocular discomfort, dryness, grittiness, burning, and stinging. Subjects are asked to grade their discomfort on a 5-point scale where 0 is no discomfort and 4 is constant discomfort ([Stonecipher, 2016](#)).

Visual Analog Scale (VAS) of Eye Dryness: The VAS is a 7-item, patient-reported symptom index with items of eye dryness, burning/stinging, itching, foreign body sensation, eye discomfort, photophobia, and pain. Subjects are asked to subjectively rate each ocular symptom by placing a vertical mark on the horizontal line from 0 to 100 (0 = no discomfort, 100 = maximal discomfort) to indicated their level of discomfort ([Holland, 2017](#)).

7.1.3. Corneal and Conjunctival Staining Score

Corneal and conjunctival staining using fluorescein or lissamine green dye is an objective assessment of the inferior, superior, central, and total regions of the cornea as well as the nasal,

temporal and total regions of the conjunctiva. Both fluorescein and lissamine green scores are obtained using the Ora Calibra™ Scale for each region that is scored from 0 to 4 where 0 = none and 4 = confluent.

7.1.4. T-Cell Assessments

Blood samples for T-cell assessments (T-cell effector total number, T-cell regulatory, and regulatory/effector T-cell ratio) will be collected at specified times during the study and shipped to a central laboratory. Detailed instructions for the collection, handling, storage and shipment of the samples will be provided in a separate laboratory manual.

7.2. Safety Assessments

All safety assessments will be performed at times outlined in the Schedule of Study Events ([Table 1](#)). Safety assessments that will be evaluated include adverse events, ophthalmic examinations, physical examination, clinical laboratory test results, metabolic panel, pregnancy testing, and vital signs.

Additional (unscheduled) safety assessments may be performed as needed.

7.2.1. Medical, Ophthalmic, and Surgical History

Medical, ophthalmic, and surgical history will be obtained at the Screening Visit. Medical history will include a review of the following systems: general, dermatological, respiratory, cardiovascular, gastrointestinal, genitourinary, gynecological, endocrine, musculoskeletal, hematological, neuropsychological, immune (allergies), and head, eyes, ears, nose, and throat. Historical and current medical conditions including date of last menstrual period for female subjects will be recorded.

Ophthalmic history will include the date and approximate time of onset, suspected cause, symptoms, course, laterality, and any treatment (drug name, dose, how administered, tapering scheme) for the current keratitis episode; and the date of any previous episodes with treatment given and response to treatment; as well as any previous or antecedent ocular trauma or surgery and any previous or antecedent ocular conditions.

7.2.2. Physical Examination

The complete physical examination will include evaluation of the head, eyes, ears, nose, throat, neck (including thyroid), cardiovascular system (including assessment of heart, peripheral pulses, presence or absence of edema), lungs, abdomen (including liver and spleen, bowel sounds), lymph nodes, musculoskeletal system (including spine, joints, muscles) neurological system (including cranial nerves, reflexes, sensation, strength), skin, extremities, and other conditions of note.

The findings of the physical examinations will be recorded. Any change from the Screening Visit physical examination that is considered clinically significant by the investigator will be recorded as an AE.

7.2.3. Height and Weight

Height and weight will be collected at baseline (Visit 2), Visit 6, and Early Termination.

7.2.4. Vital Signs

Vital signs will be obtained after the subject has been seated for 5 minutes (minimum) and will include systolic and diastolic blood pressures, pulse rate, respiratory rate, and body temperature. The results, date, and time for all vital sign assessments will be recorded. Additionally, at the Screening and Baseline Visits, blood pressure will be measured with an average of 2 readings, with at least 5 minutes between assessments after the subject has been seated for a minimum of 5 minutes prior to the initial blood pressure assessment. A subject with systolic blood pressure > 150 mm Hg and diastolic blood pressure > 90 mm Hg (average of 3 assessments) at the Screening or Baseline Visits does not qualify for the study (Section 4.2).

If an on-study systolic blood pressure is > 150 mm Hg and diastolic blood pressure is > 90 mm Hg, an AE will be recorded if the investigator determines the change is clinically significant or requires a change in the subject's clinical management.

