Study procedures	Visit 1 Screening Day -28 to-1	Visit 2 Baseline Day 1	Visit 3 Phone Day 15 ±1	Visit 4 In Clinic Day 29 ±2	Visit 5 In Clinic Day 43 ±2	Visit 6 In Clinic Day 85 ±3	Visit 7 In Clinic / End of Acthar Taper Day 113 ±3	Early Termination
Superior, central and total corneal staining score (fluorescein)	X	X		X	X	X		X
Nasal, temporal and total conjunctival staining score (lissamine green)	X	X		X	X	X		X
Schirmer's Test	X	X		X	X	X		X
IOP	X					X	X	X
Undilated Fundoscopy	X					X	X	X
Inclusion/Exclusion criteria review	X	X						
Height ^a and weight	X	X				X	X	X
Vital signs ^b	X	X		X	X	X	X	X
Physical examination	X					X		X
Laboratory testing								
Chemistry and others ^c	X	X		X	X	X		X
HbA1c	X	X		X	X	X		X
Serum Pregnancy	X	X		X	X	X		X

Study procedures	Visit 1 Screening Day -28 to-1	Visit 2 Baseline Day 1	Visit 3 Phone Day 15 ±1	Visit 4 In Clinic Day 29 ±2	Visit 5 In Clinic Day 43 ±2	Visit 6 In Clinic Day 85 ±3	Visit 7 In Clinic / End of Acthar Taper Day 113 ±3	Early Termination
Hepatitis Serology ^d	X							
IGRA for TB	X							
Immunological protein assay ^e	X	X				X		X
IXRS contact	X	X		X	X			X
Study Therapy								
Study drug and injection record training		X						
Dispense study drug		X		X	X			
Administer first dose in clinic ^f		X						
Adverse event assessment	X	X	X	X	X	X	X	X
Injection record review				X	X	X	X	X
Concomitant treatment review		X	X	X	X	X	X	X
Start Acthar Taper						X		
End Acthar Taper							X	
Study exit							X	X

AE = adverse events; ET = early termination; HbA1c = glycosylated hemoglobin; IDEEL = Impact of Dry Eye on Everyday Life; IGRA = Interferon gamma release assay; IOP = Intraocular Pressure; ODS = Ocular Discomfort Score; TB = tuberculosis; VAS = Visual Analogue Scale.

^a Height at screening only. Weight at screening, Visits 2, 6, and ET.

^b Blood pressure, respiratory rate, pulse rate and body temperature. For blood pressure, an average of 2 readings after the subject has been seated for \geq 5 minutes at the Screening and Baseline Visits. Single readings after subject has been seated for \geq 5 minutes at all other time points.

^c Refer to Section 9.2.

^d HBsAg, HBcAb, and HCV.

^e Refer to Table 2.

^f The first dose will be administered at the clinic and the subject should be observed for at least 1 hour after dosing.

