8. If male with reproductive potential, agree to use 2 forms of effective contraception (abstinence, surgical sterilization [vasectomy], or condom with spermicide) with a female partner for the duration of the study (through Visit 6);
9. Subjects must have a mean systolic blood pressure \leq 150 mm Hg and a diastolic blood pressure of \leq 90 mm Hg determined by the average of 2 seated readings taken at least 5 minutes apart at the Screening and Baseline Visits;
10. Be able to communicate effectively with study personnel;
11. Be able and willing to follow all protocol requirements and study restrictions;
12. Be able and willing to return for all study visits

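### Blood pressure rules: Section 7.2.4 averages 3 readings where 2 are taken, it and exclusion 26g are weaker than Inclusion 9, and the on-study adverse event prompt skips isolated rises

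*Combined protocol and SAP*

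**What the plan says.** **Entry.** Inclusion 9 (Section 4.1) begins "Subjects must have a mean systolic blood pressure", sets limits of at most 150 mm Hg systolic and at most 90 mm Hg diastolic, and says the value is "determined by the average of 2 seated readings taken at least 5 minutes apart at the Screening and Baseline Visits". Exclusion 26g (Section 4.2) rules out a subject above 150 systolic and above 90 diastolic, on an average of 2. Section 4.3 makes anyone who misses any eligibility criterion a screen failure.

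Section 7.2.4 says that at Screening and Baseline "blood pressure will be measured with an average of 2 readings". The next sentence disqualifies "A subject with systolic blood pressure > 150 mm Hg and diastolic blood pressure > 90 mm Hg (average of 3 assessments"); such a subject "does not qualify for the study (Section 4.2"). Footnote b to Table 1 gives, for the same two visits, "For blood pressure, an average of 2 readings after the subject has been seated for" at least 5 minutes.

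**During the study.** Footnote b continues "Single readings after subject has been seated for" at least 5 minutes at all other time points. The AE prompt in Section 7.2.4 opens "If an on-study systolic blood pressure is > 150 mm Hg and diastolic blood pressure is > 90 mm Hg". An AE is then recorded if the investigator judges the change clinically significant or in need of a change in management.

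**Stopping.** Section 6.1 requires permanent discontinuation for elevated blood pressure, but defines it as systolic not above 180 and diastolic not above 100 mm Hg.

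**The concern.** There are two points of different kinds.

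(A) The eligibility wording is wrong as written. No third reading is scheduled, so an average of 3 cannot be formed from the planned measurements. The connector is also wrong: the complement of requiring both values within limits is that *either* exceeds its limit, and 26g and Section 7.2.4 say *and*. Section 7.2.4, where staff look when measuring, sends them to Section 4.2, which holds the weaker wording, and not to Inclusion 9. A site checking only those places could pass a subject whom Inclusion 9 bars. Section 4 allows no waivers, so that would be an eligibility deviation.

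(B) The on-study prompt is a narrow trigger, not a contradiction, because Inclusion 9 applies only at Screening and Baseline. Section 1.3 lists elevation in blood pressure among the drug's common reactions, and AE incidence is a safety endpoint in Section 8.3.2. With a prompt that needs both limits to be exceeded, sites may differ in whether they record an isolated systolic or diastolic rise. The neighbouring prompts carry no joint condition: Section 7.2.2 covers any clinically significant change on physical examination, and Section 7.2.5 has every out-of-range laboratory value assessed.

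**Working it through.** No sample size, power or event figure is involved. The check compares sentences and tests their logic.

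**Reading count at Screening and Baseline**

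- 2 readings: Inclusion 9, exclusion 26g, Table 1 footnote b, and the Section 7.2.4 sentence just before the eligibility sentence.
- 3 readings: the Section 7.2.4 eligibility sentence only.

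So four places say 2 and one says 3.

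**Connector.** Let S be systolic and D diastolic.

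- Inclusion 9 is met if S ≤ 150 and D ≤ 90. It fails if S > 150 or D > 90.
- Exclusion 26g and both Section 7.2.4 sentences (eligibility and AE prompt) apply if S > 150 and D > 90.

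| S/D | Fails Inclusion 9 | Meets the *and* wording | Would meet *or* wording |
|---|---|---|---|
| 150/90 | no | no | no |
| 170/85 | yes | no | yes |
| 140/100 | yes | no | yes |
| 151/91 | yes | yes | yes |

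There are three ways to breach Inclusion 9: systolic only, diastolic only, or both. The *and* wording catches one of them and *or* catches all three.

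A check on every whole-number pair with S from 100 to 200 and D from 60 to 120 agrees. The *and* wording differs from Inclusion 9 in 3,080 pairs: 50 × 31 = 1,550 with only systolic high, plus 51 × 30 = 1,530 with only diastolic high. The *or* wording differs in 0. These are counts of number pairs, not of subjects.

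For (B), the fourth column shows which on-study readings an *or* prompt would pick up: 170/85 and 140/100 are added, and 151/91 is already covered.

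**Stopping rule in Section 6.1**

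- As printed, it applies if S ≤ 180 and D ≤ 100. A reading of 150/90 meets it and 190/105 does not. Every subject who satisfies Inclusion 9 satisfies it at entry, since 150 ≤ 180 and 90 ≤ 100. The direction is therefore inverted.
- Assuming that more than 180 and more than 100 are meant, 190/105 meets either connector, while 190/95 and 170/105 meet *or* but not *and*. The connector matters there too.

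**The case against.** On (A), the best reply is that 26g and Section 7.2.4 are weaker and redundant, and do not compete with Inclusion 9. They bar a subset of those whom Inclusion 9 already bars, and Section 4.3 requires all criteria to be met. Exclusion 27 also lets the investigator refuse a subject put at risk by any clinically significant disorder. This stands. A reader might infer that subjects with an isolated high reading can enter the trial; the documents do not support that. What remains is a wrong number and loose wording in the section that sites use when they measure.

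On (B), the reply is that the prompt only precedes a judgement. A clinically significant isolated rise can already be recorded under the AE definition in Section 9.3.2 and the recording duty in Section 9.3.4. Readings are recorded (Section 7.2.4), listed and summarised (Section 8.3.2), and the data are reviewed by the medical monitor (Section 9.1.7). This also stands, so the inference that isolated rises would be lost is not supported. Because the judgement is kept, *or* would not remove all variation between sites; it would ensure that the question is asked.

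It may also be said that the emphasised *and* in Section 6.1 shows that a joint on-study trigger is deliberate. It does not. It joins two upper limits in the form of an acceptable range, and such a range is breached when either limit is exceeded. A rule printed in the wrong direction cannot settle what was intended.

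**Conclusion.** Minor, in two parts.

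(A) holds as a drafting error of low consequence: one wrong reading count, and two sentences (26g and the Section 7.2.4 eligibility sentence) weaker than Inclusion 9. Correct application of the whole protocol still excludes these subjects, so the harm is limited to possible site error. The per-protocol population in Section 8.2 drops subjects with major deviations, but the documents do not say whether this deviation would be major.

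(B) holds as a cheap safety improvement: one sentence gives no specific AE prompt for an isolated rise, on a drug with a known pressor effect.

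The documents give no blood pressure distribution, so no rate follows. In particular, catching one of three breach patterns must not be read as missing two thirds of breaches. No efficacy analysis is affected. The reading of Section 6.1 rests on the assumption that exceeding 180 or 100 is what was meant, which only the sponsor can confirm.

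**What to change.** - Section 7.2.4, eligibility sentence: change the average of 3 to an average of 2.
- Section 7.2.4, eligibility sentence, and exclusion 26g: change *and* to *or*, so that systolic above 150 mm Hg or diastolic above 90 mm Hg excludes, matching Inclusion 9.
- Section 7.2.4, on-study sentence: change *and* to *or*, and keep the investigator's judgement of clinical significance or need for a change in management.
- Section 6.1, in the same edit: restate the stopping rule as systolic more than 180 or diastolic more than 100 mm Hg, subject to the sponsor confirming that either limit alone is meant.

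Apart from Section 6.1 this is four word changes (one number, three connectors), with no new data. The eligibility edits do not change who may enter. The on-study edit brings some extra single readings to assess and possibly more AEs recorded; the documents do not allow that number to be estimated.
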